8.0 Risks

PSG and ambulatory (actigraphy) monitoring devices are typical clinical outpatient procedures that pose mild risks that include but are not limited to: the attachment and removal of monitoring electrodes may cause mild, temporary discomfort; participants may have difficulty sleeping while the monitoring equipment is attached; participants may experience mild frustration maneuvering around equipped devices; location where sensors are worn or applied may experience temporary skin irritation. It is possible that wearing monitoring equipment may be bothersome enough to interfere with sleep quality (although that is not an intended purpose of any monitor/intervention in this research), which could make subjects feel irritable or more tired during the day time.

To minimize these risks, we thoroughly clean devices between subjects, spread out overnights involving PSG, and can adjust the application site of some sensors as-needed based on reported subject comfort/reactivity.

Participants may feel uncomfortable answering some survey questions. Participants may elect to not answer any survey question that they do not want to, but not answering may affect their study eligibility to initiate or continue in the study, or to be included in research data analyses.

Blood draws often cause mild pain, swelling or bleeding. Fasting before blood draws may be uncomfortable. There may be some bruising (blood under the surface of the skin), which can be minimized by pressing on the site after the needle is removed. There is also a small chance of infection, dizziness, or fainting. These risks will be minimized, and most likely eliminated, by having trained CRC staff perform the blood draw on a seated or reclined participant using sterile supplies. If dizziness or fainting occurs, the symptoms will be alleviated by closely monitoring the participant, directing them to lie flat with their feet raised, and by offering a snack and/or beverage. Participants demonstrating these symptoms may be asked to stay at the blood draw location (i.e. PSU CRC) or to permit study staff to stay at the blood draw location (i.e. in their personal residence) until staff have confirmed that the participant is well enough.

Use of the Frequen-ZZZ Sleep Pad may cause perceived warmth (although the pad does not emit heat) that may affect sleep. If sleep is successfully deepened by Sleep Pad system use, a device user may experience temporary drowsiness, dizziness, or disorientation upon awakening from deeper sleep (called sleep "inertia"). There is a risk of fall resulting from these sensations. To mitigate this risk, participants will be encouraged to complete their Morning Survey on their phone prior to getting out of bed in the morning, to encourage time for these possible sensations to pass. Participants will also be encouraged to take care if getting out of bed after awakening during the night. Participants are instructed on the optional procedure to pause the Sleep Pad controller during nocturnal awakenings, and this procedure is included in their Quick Reference Guide; this also should facilitate time/care taken upon awakening from Sleep Pad use.

Although it is rare, improper use of the Frequen-ZZZ sleep pad may lead to mild negative side effects, including headaches for short periods of time, restlessness, nausea, and/or perspiration. Participants will be instructed on proper use of the sleep pad at consent, will be reminded of proper use in-person prior to each Intervention/Control study phase, and will be provided with an instructional sheet to take along with them for reference at home. The Sleep Pad has undergone testing by F2 Labs and complies with FCC standards for human exposure to electromagnetic/radio-frequency emissions and some additional emissions regulations (please refer to CATS attachments, "FCC Compliance Test Statement" and "Electromagnetic Field Safety Testing"). The Sleep Pad has not be evaluated under certain conditions, and so should not be used together with other powered equipment (i.e. heated blankets or similar). The Sleep Pad should not be used on a water bed.

There is a risk of loss of confidentiality if participant information or identity is obtained by someone other than the investigators, but precautions will be taken to prevent this from happening. The confidentiality of participant electronic data created by participants or by the researchers will be maintained as required by applicable law and to the degree permitted by the technology used. Absolute confidentiality cannot be guaranteed.

9.0 Adverse Event Reporting

9.1 Adverse Event Definitions

For device studies, incorporate the following definitions into the below responses, as written:

Unanticipated	Any serious adverse effect on health or safety or any life-threatening problem
adverse device	or death caused by, or associated with, a device, if that effect, problem, or
effect	death was not previously identified in nature, severity, or degree of incidence
	in the investigational plan or IDE application (including a supplementary plan
	or application), or any other unanticipated serious problem associated with a
	device that relates to the rights, safety, or welfare of subjects.

9.2 Recording of Adverse Events

•

The study procedures involve frequent contact between study staff and participants. Research subjects will be routinely questioned about adverse events at such study visits, and relevant responses will be documented by study staff. Relevant events will be advanced to the PI consistent with an Event Reporting SOP on which staff are trained. The PI determines whether advanced events meet criteria for immediate reporting to IRB and maintain documentation of all events for annual IRB reporting.

All adverse events (serious or non-serious) and abnormal findings observed or reported to study team believed to be associated with the study drug(s) or device(s) by the PI will be followed until the event (or its sequelae) or the abnormal test finding resolves or stabilizes at a level acceptable to the Investigators. Resolution will be documented.

An abnormal finding will be classified as an adverse event if one or more of the following criteria are met:

- •The finding is accompanied by clinical symptoms
- •The finding necessitates additional diagnostic evaluation(s) or medical/surgical intervention; including significant additional concomitant drug treatment or other therapy

NOTE: Simply repeating a test finding, in the absence of any of the other listed criteria, does not constitute an adverse event.

- •The finding leads to discontinuation of subject participation in the clinical research study
- •The finding is considered an adverse event by the Investigators.

An unanticipated adverse device effect will also constitute an "abnormal finding", defined as: Any serious adverse effect on health or safety or any life-threatening problem or death caused by, or associated with, a device, if that effect, problem, or death was not previously identified in nature, severity, or degree of incidence in the investigational plan or IDE application (including a supplementary plan or application), or any other unanticipated serious problem associated with a device that relates to the rights, safety, or welfare of subjects

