3.3.2 Follow-up for withdrawn subjects

Safety data would be necessary with early withdrawal only in the case of an adverse event. Participants who withdraw from the study prior to completion and who were already randomized at the time of their withdrawal will be offered a survey similar to those completing the study to assess both their awareness of their assigned condition order and so that they have the opportunity to request to be contacted with information about their randomized order after the study concludes (please refer to CATS attachment, "End of Study Survey"). Study participants who withdraw early from the study will also be offered the same optional Follow-Up survey that is offered to completed participants.

Study participants who withdraw early from the study may or may not be eligible to participate again at a later time, depending on the reason for, and timing of, early withdrawal.

There are not any known risks to participants related to truncation of the study intervention (sleep pad use) in excess of those present prior to participation.

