6.2 Study Procedures

General overview

Participants complete Screening Consent in REDCap and, if eligible based on screening surveys, schedule their consent appointment and study dates.

Participants complete an Informed Research Consent in-person with study staff. Participation in the ~8wk study begins immediately after completion of this consent.

Throughout the entire ~8wk study:

- -Ambulatory sleep measurement (via wrist-worn actigraphy, day and night ~24hrs)
- -Twice daily self-assessment of sleep, related activities, and device usage (via REDCap sleep diaries [~1min each, totaling ~2min daily]) administered in the morning ("Morning" survey in CATS) and evening ("Bedtime" survey in CATS)
- -Weekly REDCap surveys (participants receive survey link at either/both their personal email or phone number [by text message], according to their preference; ~15min each). Participants may choose to receive email or text message reminders, or phone/voicemail reminders, to their personal accounts/devices about surveys
- -Responding to questions by staff during each study visit to determine ongoing qualification and possible study events

Overview of 4 study parts (details in below, specific sections):

- -"Baseline": Baseline data collection without sleep pad device present/in-use (week ~1) and randomization. Objective sleep monitoring for 2 nights. Blood sample (up to 40cc / up to 3 tablespoons) collected.
- -"Phase 1": Active intervention/control with either the sleep pad or an identical-looking/operated 'sham' pad present/in-use nightly (weeks ~2-4). Objective sleep monitoring for 2 nights. Blood sample (up to 40cc / up to 3 tablespoons) collected.

- -"Washout": Break from presence/use of the sleep pad device (week ~5)
- -"Phase 2": Active intervention/control with either the sleep pad or an identical-looking/operated 'sham' pad present/in-use nightly (weeks ~6-8). Objective sleep monitoring for 2 nights. Blood sample (up to 40cc / up to 3 tablespoons) collected.

All participants will complete all parts of the study (i.e. both intervention and control) but the order in which they experience these conditions will be randomized at the end of Baseline week after verifying compliance with study procedures and eligibility to continue.

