6.2.7 Visit 7 - Phase I Start: Intervention or Control

Near the end of the 3rd study week, participants have an in-person study visit to be equipped with abbreviated PSG monitoring. Overnight recording is initiated.

Above procedures take about 1 hour 'active' engagement to complete.

-Participant returns home (if applicable) and is continuously monitored throughout the subsequent remaining day and overnight with PSG

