6.2.13 Visit 13 – Phase 2 Start: Intervention or Control

Near the end of the 7th study week, participants have an in-person study visit to be equipped with abbreviated PSG monitoring. Overnight recording is initiated.

Above procedures take about 1 hour 'active' engagement to complete.

-Participant returns home (if applicable) and is continuously monitored throughout the subsequent remaining day and overnight with PSG

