6.4.4 Subject Compliance Monitoring

Participants will complete nightly REDCap surveys self-attesting adherence to the protocol during Control/Intervention (Phases 1 & 2) that are shared with the research team as data to confirm Sleep Pad use.

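### As described, adverse-event questioning is tied to study visits, but no visit falls in about the first 11 to 13 of 21 device nights of either phase, and no safety question is described at withdrawal

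*Combined protocol and SAP*

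**What the plan says.** Section 9.2 of the combined protocol and SAP starts from the premise that staff see participants often, and then says how events are elicited: "Research subjects will be routinely questioned about adverse events at such study visits, and relevant responses will be documented by study staff". The overview in Section 6.2 agrees, listing among the activities that run through the whole study: "Responding to questions by staff during each study visit to determine ongoing qualification and possible study events".

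The other instruments are described as serving different purposes. The diaries are for "Twice daily self-assessment of sleep, related activities, and device usage". The nightly device-phase surveys in Section 6.4.4 attest adherence. Of the weekly surveys, Section 6.2 describes the insomnia and pain measures.

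The schedule around first use of each controller is as follows.

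- **Phase 1.** The device is handed over at Visit 6, which closes Baseline (Section 6.2.6). The next visit is in Section 6.2.7: "Near the end of the 3rd study week, participants have an in-person study visit to be equipped with abbreviated PSG monitoring".
- **Phase 2.** The second controller arrives at the beginning of week 6, in person, by mail or by pickup, and Section 6.2.12 says that this need not be a visit. The next visit is in Section 6.2.13: "Near the end of the 7th study week, participants have an in-person study visit to be equipped with abbreviated PSG monitoring".

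On early withdrawal, Section 3.3.2 states: "Safety data would be necessary with early withdrawal only in the case of an adverse event". Randomised participants who leave are offered a survey described as covering awareness of condition order and a request to be told it later, plus an optional follow-up survey.

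Section 8.0 names the effects to look for. If sleep is deepened, "a device user may experience temporary drowsiness, dizziness, or disorientation upon awakening from deeper sleep", with a risk of falling. It also names perceived warmth and, from improper use, headache, restlessness, nausea and perspiration, which it calls mild and rare.

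**The concern.** Scheduled contact stops just as a participant begins to sleep on the device. The effects named in Section 8.0 are mostly brief. A question put about two weeks later depends on memory, and anything that should prompt staff attention arrives late unless the participant speaks up. Two other parts of the plan depend on events being known: the FDA reporting clock in Section 9.4.1 runs from notice, and the case for discontinuing the study in Section 9.7 rests on events that have been recognised.

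Withdrawal is the sharper problem. Someone who leaves before Visit 7 has not been asked about events since receiving the device. Someone who leaves before Visit 13 has not been asked since starting the second controller. Section 3.3.2 then makes safety data conditional on an event whose presence nobody is told to establish. Those who withdraw are replaced (Sections 4.2.3 and 6.4.3), so the tolerability picture could come mainly from those who stayed. With 10 planned completers, each participant is worth about 10 percentage points (1/10), and feasibility is a stated purpose of the pilot (Section 7.2).

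**Working it through.** **1. The plan's own figures.** Section 6.3 gives 17 sessions and about 15 hours. By part: 6 + 5 + 1 + 5 = 17 sessions, and 4.5 + 5 + 0.5 + 5 = 15 hours. Both reproduce, so the schedule is being read as intended. Section 6.3 also says that device-phase time falls mainly in weeks 3 and 4 and in weeks 7 and 8, which agrees with the visit texts.

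**2. Day numbering.** Study week w covers days 7(w − 1) + 1 to 7w. Section 6.1 puts the device phases in weeks 2 to 4 (days 8 to 28, 21 nights) and weeks 6 to 8 (days 36 to 56, 21 nights).

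**3. First visit after exposure starts.** Assumption: near the end of a week means its last three days. Visit 7 is then on days 19 to 21 and Visit 13 on days 47 to 49.

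**4. Nights before the first scheduled question** = visit day − first device day.

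| Phase | First device day | Next visit | Nights before it | Share of 21 |
|---|---|---|---|---|
| 1 | 8 | day 19 / 20 / 21 | 11 / 12 / 13 | 52% / 57% / 62% |
| 2 | 36 | day 47 / 48 / 49 | 11 / 12 / 13 | 52% / 57% / 62% |

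Over both phases this is 22 to 26 of 42 nights. If Visit 6 fell on day 7 and the device was used that evening, Phase 1 would gain one night (12 to 14), which changes nothing of substance.

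**5. Do Visits 6 and 12 close the gap?** No. Both come before exposure in the phase that they open. If Visit 12 is done by mail, the interval from Visit 11 (taken as day 28) to Visit 13 is 47 − 28 = 19 to 49 − 28 = 21 days without a scheduled staff question. With the anticipated maximum pause of 10 weeks it is 19 + 70 = 89 to 21 + 70 = 91 days. Part of the shorter interval, and most of the longer one, is off-device time, so these figures describe contact and not exposure.

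**6. Withdrawals in the window.** The documents give no dropout rate. If each of 10 participants had probability p of leaving in such a window, the chance of at least one is 1 − (1 − p)^10: 40% for p = 5%, 65% for p = 10%, 89% for p = 20%. These are assumed values. They say how often the withdrawal rule would come into play, and nothing about whether an event occurred.

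**The case against.** A reader might infer that visits are the only route by which an event can reach the record. The documents do not say so. Section 9.2 covers events observed or reported to the team, Section 9.4.1 covers volunteered effects, and participants have staff contact details. So it does not follow that a fall in the first nights would wait two weeks for attention; that happens only if the participant says nothing.

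A reader might also infer that early events go unrecorded in general. Participants who continue are asked at Visit 7 or Visit 13, so for them the loss is timeliness and recall.

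On withdrawal, Section 9.2 counts an abnormal finding that leads to discontinuation as an adverse event, and Section 3.3.2 lets re-entry depend on why the person left. Both presuppose that the reason becomes known. This narrows the point, but neither passage provides a step for asking.

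The diaries, weekly surveys, exit and follow-up surveys and the event-reporting procedure are attachments that were not available. Any of them may already contain an adverse-event question. Only part of the content of a weekly survey lasting about 15 minutes is described. This objection stands and limits the confidence. Section 8.0 also describes several effects as rare, mild and linked to improper use, and Section 9.7 records that the investigators consider the study minimal risk. That bears on the likely number of events, not on whether they would be captured.

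**Conclusion.** The point holds in a limited form. As described, active questioning takes place at visits, and about 11 to 13 of 21 device nights (52% to 62%) in each phase pass before the first one. For participants who continue, the consequence is delay and poorer recall of brief effects unless they volunteer them. For those who withdraw before that visit, no step is described to ask whether an event occurred, and safety data are required only if one did. The documents do not support a figure for the number of events that would be missed.

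The nights rest on device use starting on days 8 and 36 and on reading near the end of a week as its last three days. The rest depends on the survey attachments containing no adverse-event item, which could not be checked, so confidence is moderate.

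Two inconsistencies should be reconciled at the same time. The titles of Sections 6.2.7 and 6.2.13 mark the start of each phase while their texts place the visits near the end of weeks 3 and 7. Section 8.0 promises an in-person reminder of proper use before each phase while Section 6.2.12 allows the second controller to be mailed.

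**What to change.** 1. **Sections 9.2 and 6.2.** Add a short fixed adverse-event item to the weekly REDCap survey that is already sent throughout the study: the Section 8.0 effects including falls, an open option for anything else, and the date of onset. Flag positive answers to staff. If an existing form already does this, say so in Section 9.2 and name the form. A weekly item cuts the longest interval between questions in a device phase from about two weeks to about 7 days, and the Baseline and Washout surveys supply an off-device comparison.
2. **Section 3.3.2.** Replace the conditional sentence so that every participant who received a controller is asked the same item and the reason for leaving at withdrawal, using the exit survey already offered. Report these events by condition for all randomised participants, including those who were replaced.

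The cost is a minute or so per survey, staff time to review flagged answers and an IRB modification. More minor events will be recorded, because a prompted list collects what participants would not have mentioned.

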9.3 Causality and Severity Assessments

The investigator will promptly review documented adverse events and abnormal test findings to determine 1) if the abnormal test finding should be classified as an adverse event; 2) if there is a reasonable possibility that the adverse event was caused by the study drug(s) or device(s); and 3) if the adverse event meets the criteria for a serious adverse event.

If the investigator's final determination of causality is "unknown and of questionable relationship to the study drug(s) or device(s)", the adverse event will be classified as associated with the use of the study drug(s) or device(s) for reporting purposes. If the investigator's final determination of causality is

"unknown but not related to the study drug(s) or device(s)", this determination and the rationale for the determination will be documented in the respective subject's case history.

9.4 Reporting of Adverse Reactions and Unanticipated Problems to the FDA

9.4.1 Written IND/IDE Safety Reports

The Sponsor-Investigator will submit a completed FDA Form 3500Ato the FDA's Center for Devices and Radiological Health for any observed or volunteered adverse effect that is determined to be an unanticipated adverse device effect. A copy of this completed form will be provided to all participating sub-investigators.

The completed FDA Form 3500Awill be submitted to the FDA as soon as possible and, in no event, later than 10 working days after the Sponsor-Investigator first receives notice of the adverse effect.

If the results of the Sponsor-Investigator's follow-up evaluation show that an adverse effect that was initially determined to not constitute an unanticipated adverse device effect does, in fact, meet the requirements for reporting; the Sponsor-Investigator will submit a completed FDA Form 3500Aas soon as possible, but in no event later than 10 working days, after the determination was made.

For each submitted FDA Form 3500A, the Sponsor-Investigator will identify all previously submitted reports that that addressed a similar adverse effect experience and will provide an analysis of the significance of newly reported adverse effect in light of the previous, similar report(s).

Subsequent to the initial submission of a completed FDA Form 3500A, the Sponsor-Investigator will submit additional information concerning the reported adverse effect as requested by the FDA.

9.5 Reporting Adverse Reactions and Unanticipated Problems to the Responsible IRB

In accordance with applicable policies of The Pennsylvania State University Institutional Review Board (IRB), the investigator will report, to the IRB, any observed or reported harm (adverse event) experienced by a subject or other individual, which in the opinion of the investigator is determined to be (1) unexpected; and (2) probably related to the research procedures. Harms (adverse events) will be submitted to the IRB in accordance with the IRB policies and procedures.

